7 PLANNED ANALYSES

Disposition of the patient population participating in the trial will be analysed by treatment groups and presented in the clinical trial report as a frequency-distribution. The number of patients participating in the study will also be analysed by treatment group and presented as a frequency distribution.

A frequency of patients with iPDs, also summarised by whether the iPD led to exclusion from the PPS, will be presented by treatment group for treated set. The frequency of patients in different analysis sets will also be presented for each treatment group.

For in-text tables presenting descriptive analysis of the endpoints and other variables (analysed in original scale), the set of summary statistics is: N (number of patients with non-missing values), mean, standard deviation (SD).

For end-of-text tables, the set of summary statistics is: N (number of patients with non-missing values) / Mean / SD / Min / Q1 (lower quartile) / Median / Q3 (upper quartile) / Max.

For the in-text, end-of-text and appendix tables presenting descriptive analysis of the endpoints and other variables (analysed on logarithmic scale), the respective summary statistics (e.g., gMean, gCV, etc.) will be used.

Statistical parameters will be displayed to a defined number of decimal places as specified in the BI guideline "Reporting of Clinical Trials and Project Summaries" (2). Patient level results for the calculated endpoints HOMA-IR will be presented to one decimal place.

HOMA- β will be presented as full integers. The summary statistics of these parameters will follow the aforementioned guideline.

Tabulations of frequencies for categorical data will include all possible categories and will display the number of observations in a category as well as the percentage (%) relative to the respective treatment group. Percentages will be rounded to one decimal place. The category missing will be displayed if and only if there are actual missing values. Percentages will be based on all patients in the respective patient set whether they have non-missing values or not.

In all specified statistical analyses, treatment comparisons will be made between each randomised empagliflozin group (10mg and 25mg) and placebo.

7.1 DEMOGRAPHICS AND OTHER BASELINE CHARACTERISTICS

Descriptive analysis of the following demographic variables measured at baseline will be presented:

Sex, age (years) (continuous and categories), race, ethnicity, BMI (kg/m^2) (continuous and categories), height (cm), smoking history and alcohol status, time since diagnosis of diabetes (years) (continuous and categories), background medication, background insulin type, eGFR MDRD ($\text{mL}/\text{min}/1.73 \text{ m}^2$) (continuous and categories) and UACR (mg/g) (continuous and categories). Categories for baseline characteristics are defined in [Table 6.4:1](#).

Descriptive analysis of the following variables measured at baseline will be presented:

HbA1c (%) (continuous and categories), FPG (mg/dL) (continuous and categories), weight (kg) (continuous and categories), waist circumference (cm), blood pressure (mmHg) (categories), fasting serum C-peptide, HOMA-IR and HOMA- β .

Proprietary confidential information © 2021 Boehringer Ingelheim International GmbH or one or more of its affiliated companies

Both demographic and baseline characteristics tables will be presented on treated set by treatment groups.

A summary of the number of patients in each randomisation stratum per treatment will also be shown. This will be based upon the data received from the IRT provider. Analyses will be based on actual information collected via the CRF / central laboratory, not via IRT.

7.2 CONCOMITANT DISEASES AND MEDICATION

Descriptive statistics are planned for this section of the report using the treated set. Concomitant medication use will be summarised by Anatomical-Therapeutic-Chemical classification level 3 (ATC3) and preferred name. Summaries will be presented for concomitant therapies taken during screening, taken during randomised treatment and those taken at baseline. Separate summaries of antidiabetic treatment at enrolment, use of antihypertensives, acetylsalicylic acid (ASA) or lipid lowering drugs at enrolment by preferred name will be presented. The display categories and defining ATC levels and ATC code are shown in [Section 9.1](#).

Concomitant diseases will be summarised by Medical Dictionary for Regulatory Activities (MedDRA) system organ class (SOC) and preferred term (PT). Relevant diabetic medical history by treatment group will also be presented. Both summaries will be presented using the treated set.

7.3 TREATMENT COMPLIANCE

Descriptive statistics are planned for this section of the report. The number and percentage of patients with overall compliance will be reported. Overall compliance will be calculated as a weighted average of reported compliance. The sum of all reported compliance over the planned visits (disregarding run-in) will be divided by the total duration (until last visit where medication is returned). The treated set will be considered. Refer to [Section 6.6.4](#) for how to handle a single missing visit date for a compliance record, in the overall compliance calculation.

If compliance is missing at more than one on-treatment visit (>1), the overall compliance will be set to missing.

If a patient prematurely discontinues from treatment, compliance will be calculated until last study medication intake. Missing compliance values for off-treatment visits will not be considered in the calculation for overall compliance.

7.4 PRIMARY ENDPOINT

The primary endpoint in this trial is the change in HbA1c (%) from baseline after 24 weeks of treatment.

7.4.1 Primary analysis of the primary endpoint

The primary analysis is a restricted maximum likelihood (REML)based mixed model repeated measures (MMRM) approach comparing the change from baseline in HbA1c after 24 weeks of treatment. The analysis will be performed on the mITT set (OC) with treatment assignment as randomized and include on-treatment HbA1C only. If a patient misses a visit,

Proprietary confidential information © 2021 Boehringer Ingelheim International GmbH or one or more of its affiliated companies

the missing data will not be imputed. The mixed effect model will handle missing data based on a likelihood method under the “missing at random” assumption.

The statistical model will be:

Change in HbA1c (%) from baseline to the end of 24 weeks

[figure not shown]
= overall mean + treatment + background therapy + baseline HbA1c +
baseline eGFR + visit + treatment-by-visit interaction + baseline HbA1c-by-
visit interaction + random error.

The analysis will include treatment (Empagliflozin 10 mg, Empagliflozin 25 mg, placebo), background therapy (insulin only, insulin with OADs), and visit as fixed classification effects, baseline HbA1c and baseline eGFR as the linear covariates, treatment by visit interaction, and baseline HbA1c by visit interaction.

[figure not shown]
For each patient, the error terms from all the visits represent the within-patient variability and are assumed to follow a multivariate normal distribution with an unstructured covariance matrix. The random error is assumed to be normally distributed with mean 0 and unknown variance σ_j^2 . If an unstructured (co)variance structure fails to converge, the following structures will be tested in order: compound symmetry, variance components and Toeplitz. The (co)variance structure converging to the best fit, as determined by Akaike's information criterion, will be used.

The Kenward-Roger approximation will be used to estimate the denominator degrees of freedom and adjust standard errors.

A hierarchical testing sequence will be used as defined in the protocol. Superiority will be tested using the p-value of the treatment effect (least-squares means) and a two-sided 95% confidence interval for the treatment difference.

Proprietary confidential information © 2021 Boehringer Ingelheim International GmbH or one or more of its affiliated companies

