##### **7.2.2.1 Primary analysis of the primary endpoint**

The primary analysis is a restricted maximum likelihood (REML) based approach using a mixed model for repeated measures (MMRM) comparing the mean change in HbA1c from baseline after 24 weeks of treatment. The analysis will include treatment (Empagliflozin 10 mg, Empagliflozin 25 mg, placebo), background therapy (insulin only, insulin with OAD), and visit as fixed classification effects, baseline HbA1c and baseline eGFR as the linear covariates, treatment by visit interaction, and baseline HbA1c by visit interaction.

The statistical model will be as follows.

HbA1c change from baseline at each on-treatment visit = overall mean

+ treatment + background therapy  
+ baseline HbA1c + baseline eGFR  
+ visit + treatment-by-visit interaction  
+ baseline HbA1c-by-visit interaction  
+ random error

Visit will be treated as the repeated measure with an unstructured covariance structure used to model the within-patient measurement.

The Kenward-Roger approximation will be used to estimate the denominator degrees of freedom and adjust standard errors. Significance tests will be based on least-squares means using a two-sided  $\alpha=0.05$  (two-sided 95% confidence intervals). The residuals are assumed to

Proprietary confidential information © 2021 Boehringer Ingelheim International GmbH or one or more of its affiliated companies

have a multivariate normal distribution with zero means and covariance matrix as specified above. The primary treatment comparisons will be the contrasts between active treatment (Empagliflozin 10 mg and 25 mg, respectively) and placebo at week 24.

The primary analysis will be performed on mITT set with patients assigned to the treatment they are randomised to and include on-treatment HbA1c values only. If a patient misses a visit, the missing data will not be imputed. And all HbA1c values measured after premature discontinuation of study drug or after rescue therapy is initiated will be set to missing. The mixed effect model will handle missing data based on a likelihood method under the "missing at random" assumption.

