### **7.5 DETERMINATION OF SAMPLE SIZE**

In the primary MMRM analysis (with excluded off-treatment and post-rescue values), the superiority of empagliflozin 25 mg and the superiority of empagliflozin 10 mg compared to placebo will be tested separately in a hierarchical order at the two-sided alpha level of 0.05.

The effective sample size is calculated from the assumed treatment effect and the assumed covariate-adjusted standard deviation based on a two-sided t-test at alpha-level of 0.05. The effective sample size corresponds to the sample size in the absence of treatment drop-out or censoring, i.e. when all patients complete the 24 week treatment period without prematurely

discontinuing treatment and without initiating rescue therapy. Censored patients still contribute some information to the analysis and are accounted for in the actual sample size. Censored patients are assumed to contribute to sample size according to the amount of information provided as a fraction of a completer. This fraction is referred to as the information content. The sample size (SS) is derived from the effective sample size ( $SS_{eff}$ ), the assumed censoring rate (CR) and the assumed information content (IC) using the following formula:

$$SS = \frac{SS_{eff}}{1 - CR(1 - IC)}$$

Based on the experience in previous studies with Empagliflozin add-on to insulin (e.g. U12-3817-01, U13-2122-01, P19-10212), it is estimated that the difference between Empagliflozin (10 mg q.d., 25 mg q.d.) and placebo in the change in HbA1c from baseline at week 24 is about 0.62% with standard deviation of 1.1%. Given those assumptions, an effective sample size of 68 patients per treatment arm will provide 90% power to detect the standardized effect size of 0.564 (0.62/1.1) based on two-sample t-test at two-sided alpha level of 0.05 for each dose group. Assuming an 8% censoring rate (including premature treatment discontinuation and rescue therapy use) and an information content of 0.4 (based on results from previous studies), 72 patients per treatment arm are needed, leading to a total of 216 patients for three treatment arms.

The sensitivity of the sample size to the different scenarios of the assumptions is shown in Table 7.5: 1. Calculations were performed using nQuery Advisor® 7.0 statistical package by Statistical Solutions Ltd.

Table 7.5: 1 Power estimates for different scenarios for the MMRM analysis at two-sided  $\alpha = 0.05$

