Treatment effect (%)	Covariate adjusted standard deviation (%)	Censoring rate	Information content	Effective sample size per treatment arm	Sample size per treatment arm	Power
0.62	1.0	0.08	0.4	68	72	94.8
0.62	1.0	0.15	0.4	66	72	94.2
0.62	1.1	0.08	0.4	68	72	90.3
0.62	1.1	0.15	0.4	66	72	89.5
0.62	1.2	0.08	0.4	68	72	84.8
0.62	1.2	0.15	0.4	66	72	83.7

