3 INTRODUCTION

As per ICH E9, the purpose of this document is to provide a more technical and detailed elaboration of the principal features of the analysis described in the protocol, and to include detailed procedures for executing the statistical analysis of the primary and secondary variables and other data.

This trial statistical analysis plan (TSAP) assumes familiarity with the Clinical Trial Protocol (CTP), including Protocol Amendments. In particular, the TSAP is based on the planned analysis specification as written in CTP Section 7 “Statistical Methods and Determination of Sample Size”. Therefore, TSAP readers may consult the CTP for more background information on the study, e.g., on study objectives, study design and population, treatments, definition of measurements and variables, planning of sample size, randomization.

SAS® Version 9.4 or later version will be used for all analyses.

Proprietary confidential information © 2021 Boehringer Ingelheim International GmbH or one or more of its affiliated companies

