7.4.4 Supplementary analysis

The same MMRM analysis method as described in [Section 7.4.1](#) will be applied on the mITT set (OC) to compare the change from baseline in HbA1c after 24 weeks of treatment between pooled Empagliflozin doses (10 mg q.d. and 25 mg q.d.) and placebo. The model includes treatment (Empagliflozin, placebo), background therapy (insulin only, insulin with OADs), and visit as fixed classification effects, baseline HbA1c and baseline eGFR as the linear covariates, treatment by visit interaction, and baseline HbA1c by visit interaction.

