7.5.2.2 Change from baseline in body weight, SBP, DBP and FPG

The MMRM models constructed for the primary endpoint will also be conducted for continuous secondary endpoints of change from baseline in body weight, SBP, DBP and FPG at week 24. Analyses will be performed on the mITT set (OC). The model will include the baseline value of the corresponding endpoint and its interaction with visit as covariates.

Proprietary confidential information © 2021 Boehringer Ingelheim International GmbH or one or more of its affiliated companies

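### If the unstructured MMRM fails to converge, every SAP fallback assumes one residual variance for all five visits, so the Week 24 standard error is pooled over visits; very unlikely to be triggered, cheap to fix

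*SAP*

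**What the plan says.** Protocol 7.2.2.1 specifies the primary MMRM "with an unstructured covariance structure used to model the within-patient measurement", with Kenward-Roger degrees of freedom and standard errors. It names no fallback.

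SAP 7.4.1 repeats the unstructured covariance and adds one: "If an unstructured (co)variance structure fails to converge, the following structures will be tested in order: compound symmetry, variance components and Toeplitz". The next sentence says that the "structure converging to the best fit, as determined by Akaike's information criterion, will be used". No heterogeneous version and no robust standard error is mentioned. The software is SAS; SAP 3 says "Version 9.4 or later version will be used for all analyses". Just before the fallback, SAP 7.4.1 writes the error variance as σ_j² without defining j.

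Other analyses inherit the clause. SAP 7.4.4 opens its pooled-dose analysis with "The same MMRM analysis method as described in" Section 7.4.1, and SAP 7.5.2.2 says "The MMRM models constructed for the primary endpoint will also be conducted for continuous secondary endpoints".

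On variability, Protocol 7.5 gives only the Week 24 assumption, a difference of "about 0.62% with standard deviation of 1.1" percentage points. Table 7.5: 1 has a single column headed "Covariate adjusted standard deviation", with one value per scenario (1.0, 1.1 or 1.2).

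**The concern.** The primary contrast is at Week 24 only, and both hierarchical tests in Protocol 7.1 use it. An unstructured covariance estimates the Week 24 variance from its own visit. Compound symmetry, variance components and Toeplitz, read in their default SAS form, each place a single variance on the diagonal. If the spread of HbA1c change differs by visit, the Week 24 standard error is then wrong: too small if the SD grows towards Week 24, too large if it shrinks.

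Neither safeguard in the paragraph helps. AIC compares only structures that share the equal-variance assumption. Kenward-Roger adjusts for estimating the parameters of the assumed covariance; it does not repair a wrong one.

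Two wording problems sit beside this. Testing structures in a stated order and choosing the best AIC are different selection rules. And if j in σ_j² is meant to be visit, the SAP assumes visit-specific variances and then lists only fallbacks that exclude them.

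**Working it through.** **The plan's own figures.** Difference 0.62, SD 1.1, 68 per arm, two-sided α 0.05 (Protocol 7.5). Two-sample t-test power is 90.37% (stated 90.3). Sample size is 68 / (1 − 0.08 × 0.6) = 71.4, so 72 per arm and 216 in total. These reproduce, and the fallback clause does not affect them.

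**The trigger.** HbA1c is measured at five on-treatment visits, so the unstructured matrix has 5 × 6 / 2 = 15 parameters, estimated from about 216 patients. In 500 simulated trials at each of 8%, 15% and 30% dropout, with 3%, 5% and 10% intermittent missing values, the unstructured fit converged every time. No failure in 1,500 gives a rule-of-three upper bound of 3 / 1,500 = 0.2%. These fits used an EM algorithm and a simplified mean model, not SAS REML.

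**If the fallback is used.** The visit SDs are assumptions, with Week 24 fixed at the protocol's 1.1. With a pooled variance,

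- SE ratio = √(mean of the five visit variances) / 1.1
- type I error = 2 × (1 − Φ(1.96 × ratio))

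The simulation column imposes the SAP rule (best AIC) on 2,500 ordinary trials per pattern: 3 × 72 patients, the SAP's model terms, 8% random censoring, correlation 0.8 between adjacent visits, REML, t with 210 df. Monte Carlo SE is 0.3 to 0.7 points.

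| Assumed SDs, Weeks 4, 8, 12, 18, 24 | Mean variance | SE ratio | Type I, formula | Type I, simulation |
|---|---|---|---|---|
| Flat: 1.1 throughout | 1.210 | 1.000 | 5.0% | 5.1% |
| Mild rise: 0.9, 0.95, 1.0, 1.05, 1.1 | 1.005 | 0.911 | 7.4% | 7.4% |
| Moderate rise: 0.8, 0.9, 1.0, 1.05, 1.1 | 0.9525 | 0.887 | 8.2% | 8.2% |
| Steep rise: 0.6, 0.75, 0.9, 1.0, 1.1 | 0.7885 | 0.807 | 11.4% | 12.9% |
| Fall: 1.4, 1.3, 1.2, 1.15, 1.1 | 1.5245 | 1.122 | 2.8% | 2.3% |

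AIC chose Toeplitz in all 12,500 trials, so the selection step gave no protection. Only relative SDs matter for type I error, so Week 24 SDs of 1.0 or 1.2 with the same pattern give the same values.

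Power in the falling pattern: true SE = 1.1 × √(2/68) = 0.1887 and 0.62 / 0.1887 = 3.287, so power = Φ(3.287 − 1.96 × 1.122) = 86.1%. With flat SDs it is Φ(3.287 − 1.96) = 90.8%.

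**Second set of assumptions.** A large-sample calculation used correlation 0.85 per 6 weeks, 8% monotone dropout and other SD patterns. Over the three fallbacks it gave 5.0% to 5.2% (flat), 6.6% to 7.1% (mild rise), 8.6% to 9.1% (moderate), 11.9% to 12.3% (steep, from 0.55) and 4.0% to 4.2% (a shallower fall, from 1.2).

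**Overall effect.** Overall type I error = (1 − p) × 5% + p × conditional value, where p is the assumed non-convergence rate. For the steep pattern (11.4%):

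- p = 0.2%: 4.99 + 0.023 = 5.01%
- p = 1%: 4.95 + 0.114 = 5.06%
- p = 5%: 4.75 + 0.568 = 5.32%

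For the falling pattern at p = 1%, it is 4.95 + 0.028 = 4.98%.

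**Heterogeneous alternatives.** In the same simulation, heterogeneous Toeplitz gave 5.1, 5.3, 4.7, 5.3 and 5.0% in the order of the table. Large-sample checks with correlations of 0.6 to 0.9 gave 3.8% to 4.7% for heterogeneous compound symmetry. Heterogeneous AR(1) gave 5.0%, or 4.1% to 4.4% if correlation decays with weeks rather than visit number. At 0.85 per 6 weeks, heterogeneous Toeplitz also fell to 4.1%, because the visit gaps are 4 and 6 weeks and it treats them as equal.

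**The case against.** The strongest objection is that the harm needs two conditions, neither documented: a failed unstructured fit, and variances that differ by visit. With 15 parameters, about 216 patients and 8% assumed censoring, failure is remote. This stands, and it is why the overall effect is close to zero.

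The conditional figures also come from ordinary trials with the fallback imposed. Datasets in which the unstructured fit really fails may behave differently; convergence failure was not simulated and Kenward-Roger was not run. This stands too. The algebra is secure; the sizes are illustrations.

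The undefined σ_j² could mean that visit-specific variances were intended. If so, the fallback list still needs correcting, because as named it does not deliver them. The public text does not settle what j is, so this cannot be called a proven contradiction.

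The multiple-imputation ANCOVA (Protocol 7.2.2.2, SAP 6.6.2) does not use this covariance. It is a sensitivity analysis, however, and does not replace the primary p-value. SAP 7.4.2, to which SAP 6.6.2 refers, is not in the public text, so further checks there cannot be excluded. The weight, blood pressure and FPG models that inherit the clause carry no confirmatory test.

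A reader might infer that the primary test runs at 11% to 13%, or that it is anti-conservative. The documents support neither: the planned analysis is unstructured, and without SDs by visit the direction is unknown.

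**Conclusion.** The point holds as a defect in a contingency rule. If the unstructured fit fails, the stated rule bases the Week 24 standard error on a variance pooled over five visits, and nothing else in the rule corrects that. With the fallback imposed and assumed SD patterns, type I error is about 7% to 13% for a rising SD, 5% for a flat one, and about 2% to 3% with power about 86% for a clear fall (about 4% for a shallow one). At an assumed non-convergence rate of 0.2% to 1%, overall type I error in the steepest pattern is about 5.01% to 5.06%.

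The conclusion rests on reading the three names in their default SAS form. The sizes rest on assumed visit SDs, correlations and non-convergence rates. Severity is at the bottom of minor: it does not put the planned primary analysis in doubt. It is still worth correcting, because the clause matters only after a failure, and it then decides the primary p-value.

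**What to change.** Before unblinding, replace the two fallback sentences in SAP 7.4.1 with:

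> If the unstructured structure fails to converge, the following will be fitted in this order and the first to converge used, with Kenward-Roger: heterogeneous Toeplitz, heterogeneous first-order autoregressive, heterogeneous compound symmetry.

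Define j in σ_j² at the same time. The replacement estimates the Week 24 variance separately, leaves one selection rule instead of two, and carries over to SAP 7.4.4 and 7.5.2.2. It needs no protocol change, because Protocol 7.2.2.1 names no fallback and its Kenward-Roger rule is kept.

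The costs are 6 to 9 covariance parameters instead of 1 to 5, and a slightly conservative test in some cases. Type I error is about 3.8% to 4.7% if heterogeneous compound symmetry is reached, and about 4.1% to 4.4% for the other two if correlation decays with weeks. The sentence does not cover failure of all the listed fits.

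Compound symmetry with a sandwich standard error should not be added as a last step. It would depart from the protocol's Kenward-Roger rule, and a sandwich error does not remove bias from a wrong covariance when rescue censoring depends on outcome. In a check with assumed dropout of 6% on placebo and 2% on active and the steep pattern, compound symmetry gave a Week 24 difference of 0.597 against 0.618 with the correct covariance; heterogeneous compound symmetry gave 0.625.
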